7.2 Sample Size and Accrual

We originally anticipated 100-150 patients to be enrolled per year. A sample size of 66 in each group will have 80% power to detect a difference in mean EORTC scores of 10.000 assuming that the common standard deviation is 22.900 using two group t-test with a 0.050 one-sided significance level. The target sample size was 140 patients to allow appropriate block randomization in groups of 20. Based on enrolling about 140 patients, we would be powered to detect an effect size of 0.437 (difference in means of 10, common standard deviation of 22.9). Due to slower accrual in context of COVID-19, we anticipate enrollment of 100-140 patients before funding ends. With 100 patients, we will have 80% power to detect an effect size of 0.501 (difference in means of 11.467, common standard deviation of 22.9). Power calculations were performed using SAS version 9.4 (SAS Inc., Cary, NC) using PROC POWER and a two sample means difference test.

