7.3 Data Analysis Plans

7.3.1 Aim 1: Impact of PRO monitoring with symptom alerts, compared to PRO monitoring without alerts, after thoracic surgery on post-operative quality of life.

Impact will be determined by comparing baseline quality of life to quality of life at the following timepoints: Day 14, Day 60, Day 120, Day 180, and Day 365 post-discharge. QOL will be measured by administering European Organisation for Research and Treatment of Cancer's (EORTC) EORTC QLQ-LC13 and EORTC QLQ-C30. These surveys will be scored according to methods described in the EORTC scoring manual: <https://qol.eortc.org/manual/scoring-manual>.

Student's T and/or Wilcoxon rank sum tests will be used to perform bivariable comparisons of EORTC scores at each of the time points (baseline/pre-operative and Day 12, Day 60, Day 120, Day 180, and Day 365 post-operative).

Additionally, a linear mixed effect model will be used to assess the average

change in EORTC scores over time amongst both groups, and the difference in average trajectory between them, after accounting for repeated measures and within- and between- subject variability. Both a random intercept and slope (for time) statement will be used, and an unstructured correlation matrix will be applied. The random intercept and slope will allow us to assess the impact of symptom alerts while allowing for random variation in baseline quality of life and trajectories.

If there are convergence issues, simpler correlation structures may be used (e.g. independent) or the random slope parameter may be dropped. Dropping the random slope parameter will mean we are assuming that there is no/minimal individual variation in trajectory across patients.

7.3.2 Aim 2: Determine feasibility of 3-month post-operative PRO symptom monitoring with alerts.

The proportion of completed symptom surveys (overall and in each arm) at 3-months postoperative will be calculated, as well as the proportion of participants who completed all surveys during that time. Chi-square, Student's T, and Wilcoxon rank sum tests will be used to compare patient demographics, study arm, and surgery characteristics between those who did and did not complete all surveys to attempt to identify predictors of compliance. Multivariable logistic regression may also be used.

Similar methods will be used to assess proportion of symptom alerts that generate a clinician response.

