7.3.3 Aim 3: Identify barriers/facilitators of PRO monitoring through semi-structured interviews.

Patient and caregiver interview transcripts will be analyzed as they are collected. Transcripts will be coded using in vivo coding methods and a code book will be created. Interviews will continue until thematic saturation is achieved, which will be defined by no new codes being generated to add to the code book.

7.3.4 Sub-Aim 1: Impact of PRO monitoring with symptom alerts, compared to PRO monitoring without symptom alerts, on post-operative readmission and mortality rates.

Kaplan Meier curves and Cox proportional hazards regression will be used to assess the impact of study treatment arm on 30-day and 90-day emergency department (ED) visits, readmissions, and all-cause mortality, as well as 1-year all-cause mortality. A linear mixed effect model will be used to assess the change in 2-year quality of life (described in Aim 1).

Patients who are lost to follow-up will be censored at their last clinician/study interaction. Mortality will be treated as a competing risk for ED visits and readmission. This aim will be approached as an intent-to-treat analysis and will not require that patients used their PRO monitoring or had symptom alerts sent to

their clinician.

7.3.5 Sub-Aim 2: Determine the feasibility of PRO monitoring for assessing quality of life.

Similar methods to Aim 2 will be used. The proportion of completed QOL surveys (overall and in each arm) at each time point (baseline/pre-operative and 2-weeks, 6-months, 1-year, and 2-year post-operative) will be calculated, as well as the proportion of participants who completed all surveys during that time. Chi-square, Student's T, and Wilcoxon rank sum tests will be used to compare patient demographics, study arm, and surgery characteristics between those who did and did not complete all surveys to attempt to identify predictors of compliance. Multivariable logistic regression may also be used.

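### The primary quality-of-life analysis in section 7.3.1 is incompletely specified: no EORTC scale, visit or contrast decides, and the per-visit tests leave baseline unadjusted

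*Combined protocol and SAP*

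**What the plan says.** Impact on quality of life is the first primary objective (2.1.1), and section 7.2 sizes the trial on it: "80% power to detect a difference in mean EORTC scores of 10.000", with SD 22.9, a two-group t-test and one-sided 5%. No scale or visit is attached to that calculation. Because accrual was slow, "we anticipate enrollment of 100-140 patients before funding ends".

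Section 7.3.1 gives two kinds of analysis.

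- **Visit comparisons.** "Impact will be determined by comparing baseline quality of life to quality of life at the following timepoints", namely Days 14, 60, 120, 180 and 365. The tests are Student's t and/or Wilcoxon, for "bivariable comparisons of EORTC scores at each of the time points", baseline included. (The second list of visits in that section has Day 12 where the first has Day 14.)
- **A mixed model, introduced as an addition.** It targets average change over time and "the difference in average trajectory between them". On its structure: "Both a random intercept and slope (for time) statement will be used, and an unstructured correlation matrix will be applied". A fallback for non-convergence is given.

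The outcome is described as "EORTC QLQ-LC13 and EORTC QLQ-C30. These surveys will be scored according to methods described in the EORTC scoring manual". No scale from either questionnaire is singled out.

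For the secondary 2-year outcome, section 7.3.4 says only: "A linear mixed effect model will be used to assess the change in 2-year quality of life (described in Aim 1").

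**The concern.** Three things are left open for the first primary objective.

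1. **What decides.** There are two questionnaires, five post-baseline visits and two kinds of analysis. No order of precedence is given, and no rule applies if they disagree.
2. **How baseline is used.** Impact is framed as a comparison with baseline. Yet the per-visit tests compare scores between arms without adjusting for baseline, and the model appears to treat baseline as one more outcome. With 100-140 patients, the power that adjustment would recover matters.
3. **What the model tests.** The form of time (linear or categorical) and the contrast of interest are not written down. In Aim 1 the visit tests stand beside the model. For 2-year quality of life nothing does, and the visits listed for the model stop a year short of that outcome.

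The result could therefore turn on choices made after the data are seen. Section 4.2 says analysis takes place throughout the study.

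**Working it through.** **Step 1. The plan's own figure.** Inputs from 7.2: difference 10, SD 22.9, one-sided 5%, two-group t-test. Noncentrality = 10 / (22.9 × √(2/66)) = 2.51. The noncentral t gives 80.3% power at 66 per arm and 79.7% at 65, so 66 reproduces. At 50 per arm the effect detectable with 80% power is 0.501, as stated.

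**Step 2. Baseline adjustment at one visit.** Assumptions not in the documents: correlation r between baseline and visit score of 0.4-0.6, complete data, and SD 22.9 applying at that visit. The effective SD is multiplied by 1 (unadjusted), √(2(1−r)) (change score) or √(1−r²) (baseline as covariate). Noncentrality = 10 / (effective SD × √(2/n)).

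| Analysis | Effective SD | Power, 70/arm | Power, 50/arm |
|---|---|---|---|
| Unadjusted, as planned | 22.9 | 82% | 70% |
| Change from baseline, if that is meant | 25.1 to 20.5 | 76-89% | 63-78% |
| Baseline as covariate | 21.0 to 18.3 | 88-94% | 76-86% |

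These powers depend on the SD. If patients' slopes varied with an SD of 20 points per year, the SD at Day 365 would be √(22.9² + 20²) = 30.4, and the unadjusted test at 70 per arm would have about 61% power there. No document supports or excludes that value.

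**Step 3. Chance findings if any favourable visit could count.** Simulated normal test statistics with no true effect, five post-baseline visits, threshold 1.645, between-visit correlation 0.4-0.6.

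- One scale: 18% (correlation 0.4) to 15% (0.6).
- One scale from each questionnaire, between-scale correlation 0.3-0.7, with the correlation across different scales and visits taken as the product of the two: 23-31%.

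**Step 4. One possible reading of the model: linear time, only the arm-by-time slope read.** Take a sustained 10-point benefit at every post-baseline visit to Day 365. The slope difference is Σ(t − t̄)δ / Σ(t − t̄)², with δ = 0 at baseline.

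- Baseline coded Day 0: t̄ = 123.2, sum of squares 92,801. Slope = 1,232 / 92,801 × 365 = 4.84 points per year.
- Baseline coded Day −90: t̄ = 108.2, sum of squares 121,721. Slope = 1,982 / 121,721 × 365 = 5.94 points per year.

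The Day −90 case is an assumption. It is prompted by section 3.2, which allows up to 3 months between consent and surgery.

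SE = √((2/n)(slope SD² + (1 − corr) × 22.9² / Sxx)), with Sxx in years². With within-patient correlation 0.4-0.6, slope SD 0-20 and 70 per arm, the SE is 2.9-4.9 (Day 0) or 2.6-4.6 (Day −90). Power = Φ(slope/SE − 1.645), which gives 25-50% and 36-75%. Over Day 0 to Day −90 the range is about 25-75%. A joint two-degree-of-freedom test of level and slope (two-sided 5%, same inputs) has 61-91%.

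The choice can also work the other way. For a benefit growing linearly to 10 points at Day 365 (correlation 0.5, no slope variation, baseline at Day 0, 70 per arm), the slope test has 92% power and an unadjusted Day 60 comparison 11%.

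**The case against.** The strongest reply is that the plan says more than a quick reading suggests. A difference in trajectory with a random slope for time implies arm, time and arm-by-time terms. Baseline is a listed time point and the random intercept is said to cover variation in baseline quality of life, so baseline most naturally sits among the outcomes. The section opens with visit comparisons, 7.2 uses a two-group t-test, and the model is an addition, which hints at a hierarchy. It would therefore be too strong to say that the plan is silent on baseline or on the model's terms. But these are inferences: the form of time, the tested contrast, the deciding visit and the scale still cannot be recovered from the text.

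A reader might infer from Step 3 that the trial has a 15-31% false-positive rate. The documents do not support that. No section says that any favourable visit or scale counts as success, so the figures describe a risk that the present wording leaves open.

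A reader might also infer that the model will miss, or even reverse, a real benefit. That needs linear time, the slope alone as the answer and a particular shape of benefit. The documents state none of these. The symptom surveys that trigger alerts end at Day 90, so a fading benefit is plausible, but no document predicts it. In Aim 1 the visit tests could still show an early effect.

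It is also fair that the trial was sized on an unadjusted test, so adjusting for baseline is an improvement and not the correction of an error. The feasibility label in 7.1 does not dispose of the point, because quality of life is the first primary objective and the one that was powered.

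**Conclusion.** The point holds as incomplete specification, and it should be fixed. No EORTC scale, visit or analysis decides Aim 1. The mixed model lacks a stated form of time and a tested contrast. The 2-year analysis rests on that model alone, with listed visits that end at Day 365.

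The gain from baseline adjustment is about 5 to 12 percentage points of power at 70 per arm and 6 to 16 at 50 per arm. It rests on a correlation of 0.4-0.6, SD 22.9 at the visit and complete data. The chance-finding figures apply only if any visit may count. The slope figures apply only under one reading of the model. The sample-size arithmetic is sound. Confidence is medium, because the omission is plain from the text but its size depends on correlations that the documents do not give.

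**What to change.** **In 7.3.1:**

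- Name one EORTC scale. A global quality-of-life score would fit the purpose statement in 4.1.
- Name one primary between-arm contrast: a visit, or an average such as Days 14-180.
- Estimate it from a model with categorical visit, arm-by-visit terms and adjustment for the baseline EORTC score.
- State that this contrast decides, and that the per-visit tests and other scales are supportive.
- Reconcile Day 12 with Day 14.

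**In 7.3.4:** name a separate 2-year contrast that uses the Day 545 and Day 730 surveys, and list those visits in the model.

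**Sensitivity analysis:** repeat the model with actual completion day. Windows are wide (the Day 180 survey may come up to 185 days late), and baseline may precede discharge by weeks to months.

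**Cost.** This is a change of wording on data already collected, but it has two real downsides.

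- An unstructured covariance over k visits needs k(k+1)/2 parameters. That is 21 for the six Aim 1 time points (15 with baseline as a covariate) and 36 for all eight administrations (28 with baseline as a covariate). The present model has 4: two random-effect variances, their covariance and a residual. With 100-140 patients, a simpler structure must be stated in advance, for example the planned random effects with robust standard errors.
- An average contrast dilutes a short benefit. Ten points at only one of the four visits from Day 14 to Day 180 averages 10/4 = 2.5, and at two visits 20/4 = 5.

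Categorical visit with baseline adjustment is one good choice among several. What matters most is that one scale and one contrast are fixed before any between-arm comparison is seen.

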2.0 STUDY OBJECTIVES AND ENDPOINTS

2.1 Primary Objectives

2.1.1 To determine impact of PRO monitoring with symptom alerts compared to PRO monitoring without symptom alerts after thoracic surgery on post-operative quality of life.

2.1.2 To determine feasibility of 90-day post-operative PRO symptom monitoring after thoracic surgery symptom monitoring eliciting a clinician response.

Feasibility is defined as:

1. $\geq 50\%$ of participants complete all symptom surveys until 3 months post-operatively
2. $\geq 50\%$ of symptom alerts generate a clinician response

2.1.3 To determine barriers/facilitators of PRO monitoring after thoracic surgery through semi-structured interviews of patients and caregivers.

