4.3 Study Details

Participants complete electronic surveys to assess their baseline and post-operative characteristics, symptoms, quality of life, and health outcomes. The study consists of a total number of 9 different surveys.

Figure 2: Survey Frequency and Duration

Survey	Frequency	Completion Time
Pre-operative Symptom Survey	1	5 minutes
Patient Demographics	1	3 minutes
PROMIS Physical Function SF 4a Survey	32	2 minutes
EORTC QLQ-LC13 survey	8	3 minutes
EORTC QLQ-C30 survey	8	8 minutes
Patient Satisfaction survey	7	3 minutes
Readmission Patient Survey	7	2 minutes
Post-operative symptom Daily Survey	15	7 minutes
Post-operative symptom Weekly Survey	11	7 minutes

Enrollment/Baseline Visit

Patients at the multidisciplinary thoracic oncology clinic with plans for thoracic surgery will be approached for enrollment based on inclusion/exclusion criteria described above. An IRB-approved study team member will approach the patient to discuss study procedures, benefits, risks and obtain informed consent prior to any study procedures. The study team member will also teach the patient how to complete the PRO assessment using PRO Core.

At that time, the participant will complete their pre-operative PRO assessment in a private area, which will include PRO surveys as well as demographic questions such as age, sex, and education. PRO survey responses will be reported using the PRO Core database. Paper copies of PRO surveys and source documents will be used if PRO Core system is inaccessible.

For patients who are found to be ineligible during screening or those potentially eligible during screening but found to be ineligible after contact, reasons for ineligibility as well as basic demographics available in the EMR (e.g. race, ethnicity, age, gender, education level if available) will be collected in PRO Core.

For patients who are eligible but refuse enrollment, reasons for refusal, as well as basic demographics available in the EMR (e.g. race, ethnicity, age, gender, education level if available) will also be collected within PRO Core.

Discharge Day (Day 0) Visit:

On the day of discharge (or the next business day in the case of late or weekend discharges), discharge day surveys will be activated in PRO Core by the study staff.

A study team member will call or approach participant in their hospital room before or after discharge to reorient the participant with PRO Core, if needed.

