Participants will be reminded of the post-discharge survey schedule, helped with any questions they may have, and assisted with completing any due surveys, if needed.

In the case the day of discharge survey is not obtained (e.g late in the day discharges, weekend discharges, and patient unable or unwilling to complete a survey), this will not be considered a protocol deviation.

The study team member activating the discharge day survey will obtain surgical information from Epic, the surgeon or surgery care team member.

Day 0 (Discharge) to Day 14 Post-Discharge

At this time the following procedures will be performed:

- Daily Post-operative symptom survey
- Daily PROMIS Physical Function SF 4a survey

Day 14 (+/- 7 days) Post-Discharge

At this time the following procedures will be performed:

- EORTC QLQ-LC13 survey
- EORTC QLQ-C30 survey
- Patient Satisfaction survey
- Readmission Patient Survey

Day 15 to Day 90 Post Discharge

Weekly symptom monitoring commences. At this time the following procedures will be performed:

- Weekly Post-operative symptom survey
- Weekly PROMIS Physical Function SF 4a survey

Day 60 Post-Discharge (+60 days)

At this time the following procedures will be performed:

- EORTC QLQ-LC13 survey
- EORTC QLQ-C30 survey
- Patient Satisfaction survey
- Readmission Patient Survey

Day 120 Post-Discharge (+60 days)

At this time the following procedures will be performed:

- EORTC QLQ-LC13 survey
- EORTC QLQ-C30 survey
- PROMIS Physical Function SF 4a survey
- Patient Satisfaction survey
- Readmission Patient Survey

Day 180 Post-Discharge (+185 days)

At this time the following procedures will be performed:

- EORTC QLQ-LC13 survey
- EORTC QLQ-C30 survey
- PROMIS Physical Function SF 4a survey
- Patient Satisfaction survey
- Readmission Patient Survey

Day 365 Post-Discharge (+180 days)

At this time the following procedures will be performed:

- EORTC QLQ-LC13 survey
- EORTC QLQ-C30 survey
- PROMIS Physical Function SF 4a survey
- Patient Satisfaction survey

Day 545 Post-Discharge (+185 days)

At this time the following procedures will be performed:

- EORTC QLQ-LC13 survey
- EORTC QLQ-C30 survey
- PROMIS Physical Function SF 4a survey
- Patient Satisfaction survey

Day 730 Post-Discharge (+185 days)

At this time the following procedures will be performed:

- EORTC QLQ-LC13 survey
- EORTC QLQ-C30 survey
- PROMIS Physical Function SF 4a survey
- Patient Satisfaction survey

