7.0 STATISTICAL CONSIDERATIONS

7.1 Study Design

This is a single center, randomized feasibility study. A total of 140 patients undergoing thoracic surgery will be prospectively enrolled and randomized in a 1:1 ratio. A random block method with blocks of 20 will be utilized to randomize participants to one of two arms to complete PRO (patient reported outcome) symptom monitoring. The two arms are 1) active symptom monitoring and 2) passive symptom monitoring. The participants randomized to active symptom monitoring will have alerts sent to their clinicians when their PRO symptom scores exceed baselines scores by 2 points or more, or when 'severe' or 'very severe' symptoms are reported. Participants randomized to the passive PRO monitoring arm will complete the same PROs as participants in the active monitoring arm, but will not have alerts sent to their clinician. All participants will be administered survey instruments to further assess quality of life including: EORTC QLQ30, EORTC LC13, PROMIS Physical Function SF 4a survey SF 4a. Additionally, in order to assess the feasibility of the PRO monitoring system, all participants will be asked to complete a Patient Satisfaction survey. In addition, a subset of 40 participants and 40 caregivers will be chosen to complete a semi-structured interview, if willing, to assess patient satisfaction with symptom monitoring experience. The subset will be made up of a range of post-operative experiences and will be a fair representation of study population, including both

study arms. Participants will be chosen by principal investigator and eligible to participate in interview after 14 days of discharge

The primary objectives are to determine 1) impact of PRO monitoring with symptom alerts compared to PRO monitoring without symptom alerts after thoracic surgery on post-operative quality of life 2) feasibility of 3-month post-operative PRO symptom monitoring after thoracic surgery symptom monitoring eliciting a clinician response 3) barriers/facilitators of PRO monitoring after thoracic surgery through semi-structured interviews of patients.

Secondary objectives include: 1) determining impact of PRO monitoring with symptom alerts compared to PRO monitoring without symptom alerts after thoracic surgery on post-operative readmission and mortality rates 2) determining feasibility of PRO monitoring after thoracic surgery in regards to monitoring quality of life.

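### Predictors of compliance are tested only on an all-or-nothing completion split; adding the number of surveys completed per participant would recover power, by an amount the documents cannot fix (minor)

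*Combined protocol and SAP*

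**What the plan says.** Section 2.1.2 sets the first feasibility criterion as at least 50% "of participants complete all symptom surveys until 3 months post-operatively". Section 2.2.2 sets a parallel all-surveys rule for quality of life (QOL).

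Section 4.3 (Figure 2) gives the number of symptom surveys per participant: "Post-operative symptom Daily Survey 15 7 minutes" and "Post-operative symptom Weekly Survey 11 7 minutes". It also allows the discharge-day survey to be missed for reasons such as a late or weekend discharge: "this will not be considered a protocol deviation".

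For Aim 2, section 7.3.2 states: "The proportion of completed symptom surveys (overall and in each arm) at 3-months postoperative will be calculated". It also calculates the share of participants who completed everything. Predictors, with study arm among them, are then examined by chi-square, t and rank-sum tests "between those who did and did not complete all surveys to attempt to identify predictors of compliance". The only extension is: "Multivariable logistic regression may also be used". No outcome is named for that model, and in context it is the same yes/no variable. Section 7.3.5 repeats this scheme for the QOL surveys.

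**The concern.** The predictor analysis asks who complies, and its list of predictors includes whether alerts change compliance. The variable used separates perfect responders from everyone else. Near-perfect responders and non-responders fall in the same group, although non-responders are the ones an implementation team most needs to recognise.

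One missed survey in 26 is enough to change a participant's class. Days 0 to 14 make 15 daily surveys, so the discharge-day survey is one of the 26. The plan does not say whether a discharge-day survey that was never obtained counts against completion. If it does, an engaged participant discharged at a weekend can become a non-completer, and the contrast partly reflects discharge timing.

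What is at stake is power for an exploratory search, in a study that may enrol only 100 patients (section 7.2). The validity of a primary result is not in question.

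**Working it through.** **What the plan gives.** It gives 26 symptom surveys (15 + 11), 140 patients 1:1 (100 to 140 anticipated), and the 50% rule. It gives no power, effect size, expected completion rate, within-patient correlation or significance level for the predictor tests. The only power figure in the documents is for mean EORTC scores, and it reproduces: (10/22.9) × √(66/2) = 2.51, and Φ(2.51 − 1.645) = 0.806 (0.8025 by noncentral t), against the stated 80%. It has no bearing on this analysis, so everything below rests on stated assumptions, with two-sided 0.05 tests.

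**Check 1: information kept by a split (latent-normal model).** If compliance is normal and cut so that a share p completes everything, relative efficiency is φ(z_p)² / [p(1 − p)].
- p = 0.50: 0.3989² / 0.25 = 0.64
- p = 0.30: 0.58
- p = 0.20: 0.2800² / 0.16 = 0.49
- p = 0.10: 0.34

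About 36% is lost at the plan's 50% threshold. More than half is lost only when about 20% or fewer complete everything.

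**Check 2: simulation with 26 surveys (logit-normal).** Each participant has a completion probability with normal logit. The count is binomial(26), and the two arms of 70 differ in mean completion. The chi-square on all versus not is compared with the rank-sum on the count.

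| Mean completion, arm difference, logit SD | Complete all 26 | Split | Count | Gap (points) |
|---|---|---|---|---|
| 80%, 8 points, 1 | 8% | 27% | 82% | 55 |
| 85%, 8 points, 1.5 | 25% | 47% | 77% | 30 |
| 85%, 8 points, 2.5 | 42% | 42% | 59% | 17 |
| 85%, 8 points, 3.5 | about 54% | 42% | 48% | 6 |
| 85%, 12 points, 3.5 | about 54% | 77% | 83% | 6 |
| 93%, 6 points, 2 | about 54% | 75% | 84% | 9 |

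Repeating every row with 4,000 trials moved no power figure by more than 3 points.

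The second row can be checked by hand. The share completing everything is the mean of p^26, which is 17.6% and 31.4% in the two arms (pooled 24.5%). The null standard error is √(2 × 0.245 × 0.755 / 70) = 0.0727. The alternative standard error is √[(0.176 × 0.824 + 0.314 × 0.686) / 70] = 0.0718. Power is Φ[(0.138 − 1.96 × 0.0727) / 0.0718] = Φ(−0.06), about 47%.

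With 100 patients the second row becomes about 34–37% v 62–64%. With no arm difference, both tests reject about 5% of the time.

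**Check 3: a different clustering model (beta-binomial, 26 surveys).** The gap against the rank-sum test ranges widely.
- Largest: means 60% v 75%, correlation 0.2, 100 patients, 39.6% v 91.8% (52 points).
- Near the smallest: means 80% v 90%, correlation 0.5, 140 patients, 79.5% v 81.4% (about 2 points). With 100 patients it is 65.5% v 66.8% (1.3 points).
- In the 140-patient case of the second bullet, a t-test on the count reaches only 61.9%, which is worse than the split. The gain belongs to the rank-based analysis, not to any analysis of the count.

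**Check 4: QOL surveys.** Section 7.3.5 lists five time points (baseline, 2 weeks, 6 months, 1 year, 2 years), while section 4.3 has eight administrations. Under the assumptions of the second row, power is about 52% v 64% with eight and 48% v 56% with five. The gain is smaller because fewer surveys leave less to discard.

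**The case against.** The best defence is that completing everything is the protocol's own criterion, in both 2.1.2 and 2.2.2. Asking which participants meet the criterion is a coherent question, and the split answers it. The analysis is also exploratory and unpowered, in a single-center feasibility study, and it is statistically valid. Low responders are not ignored elsewhere: section 4.3 purposively seeks participants with poor completion for interview, and survey-level completion is reported by arm. All of this stands. It is why the split should be kept and why the point is minor. It does not answer the narrower criticism that no specified test can tell a participant who missed one survey from one who missed them all.

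A reader might go further and infer that the split throws away most of the information, or that it takes power from about 78% to 47%. The documents support neither as a general statement. The power figures come from one assumed scenario in which about a quarter complete everything, less than half of the plan's 50% target. Where that target is met, the logit-normal gap is about 6 to 9 points. Equally, the documents give no basis for assuming high completion, so the large losses cannot be excluded.

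**Conclusion.** The point holds as a minor efficiency weakness. The predictor tests in 7.3.2 and 7.3.5 use only the all-versus-not split, although a per-participant count is available from the same data. The rank-sum test on the count had higher power in every setting shown, by between 1 and about 55 points for the 26 symptom surveys. The gap is widest when few participants complete everything and narrowest when completion is high and strongly clustered within patients. For QOL surveys it is about 8 to 12 points under the assumptions used.

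These figures rest on assumed completion rates, arm differences, between-patient spread and two-sided 0.05 testing. What the documents themselves establish is the structure: 26 surveys reduced to one yes/no, with no predictor test on survey-level completion. It would be wrong to infer that the planned tests are invalid or that the primary conclusions are at risk. Neither the Aim 1 comparison nor the 50% decisions depend on this analysis.

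**What to change.** In 7.3.2 and 7.3.5:
- Keep the yes/no outcome for the 50% feasibility rules and for describing who meets them.
- Add surveys completed out of surveys due, per participant, as the main outcome for the predictor analyses. Use rank-sum or Spearman for single predictors, and a logistic GEE or overdispersed (beta-)binomial model for the multivariable analysis. A GEE compares mean proportions, as the t-test does, so it may not share the rank test's advantage under strong clustering. That is a further reason to report the split alongside.
- Define surveys due. State whether a discharge-day survey that was not obtained counts, and reconcile the five QOL time points in 7.3.5 with the eight administrations in 4.3.

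The cost is SAP wording and one additional analysis on data already being collected.
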